Patients potentially eligible for this study are at least 18 years of age and have histologically confirmed necrobiosis lipoidica diabetorum. A total of 18 subjects will be enrolled in the study. Potential patients will be assessed for eligibility to participate in this clinical study using the criteria for inclusion and exclusion listed under “Subject Selection” section.

Methods

Study Endpoints:

1. Primary Endpoint

- **Proportion of patients achieving remission or clinical improvement based on Investigator Global Assessment Score as measured at week 24.**

2. Secondary Endpoints

- **Proportion of subjects achieving improvement based upon histological score**
- **Proportion of subjects improving based upon patient-reported outcomes (pain score and Dermatology Quality of Life Index Score)**

Investigator Global Assessment (IGA) of Efficacy Score (See Investigator Global Assessment of Efficacy Score)

(adapted from scoring system for published pyoderma gangrenosum trials)

Score	Description
0	Completely clear: except for possible residual hyperpigmentation
1	Almost clear: very significant clearance (about 90%); however, patchy remnants of dusky erythema and/or very small ulcerations
2	Marked improvement: significant improvement (about 75%); however, a small amount of disease remaining (i.e. remaining ulcers, although have decreased in size, minimal erythema and/or active boarder)
3	Moderate improvement: intermediate between slight and marked; representing about 50% improvement
4	Slight improvement: some improvement (about 25%); however, significant disease remaining (i.e. remaining ulcers with only minor decrease in size, erythema or boarder activity)
5	No change from baseline
6	Worse

Scoring system based on the following trial [4]:

An open-label pilot study of alefacept for the treatment of pyoderma gangrenosum. European Academy of Dermatology and Venereology 2008 22, pp943–949

Histological Score

- a. Inflammatory infiltrate (0, none; 1, slight; 2, moderate; 3, severe)
- b. collagen degeneration (0, none; 1, slight; 2, moderate; 3, severe)
- c. epithelioid histiocytes, (0, none; 1, slight; 2, moderate; 3, severe)
- d. qualitative expression of IL-17 (0, none; 1, slight; 2 moderate; 3, severe)

Scoring system based on the following trial [5]:

Fumaric acid esters in necrobiosis lipoidica: results of a prospective noncontrolled study. British

Journal of Dermatology 2005 153, pp802–807

Patient-Reported Outcomes

Pain Score

- _(i) Resolved

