- (ii) Improved
- (iii) Stable
- (iv) Worsened

Dermatology Life Quality Index (DLQI)

A Quality of Life Score will be calculated based upon the Dermatology Life Quality Index (DLQI). The DLQI is a validated general dermatology questionnaire that consists of 10 items that assess subject health-related quality of life (daily activities, personal relationships, symptoms and feelings, leisure, work and school, and treatment) (See Dermatology Life Quality Index). [7] It has been extensively used in dermatology clinical trials for AD. The DLQI is a psychometrically valid and reliable instrument that has been translated into several languages, and the DLQI total scores have been shown to be responsive to change. The minimally important difference for the DLQI has been estimated as a 2 to 5 point change from baseline.

Other study parameters

Safety Parameters

Safety evaluations include adverse event (AE) monitoring, physical examinations, vital sign measurements, and clinical laboratory testing (hematology and chemistry) as a measure of safety and tolerability for the entire study duration.

At every visit adverse events will be registered.

Randomization, blinding and treatment allocation

This is an open-label proof of concept study. There will be no randomization or blinding. All subjects will receive study treatment.

Study Procedures

Prior to performing any study related procedures, the investigator will discuss with each subject the nature of the study, its requirements and its restrictions. A written informed consent form will be obtained from each participant prior to any procedure.

Each subject with a signed informed consent form will be screened at the first visit, to ensure all the inclusion criteria are met and none of the exclusion criteria.

Study procedures are described in detail below and an overview of the study procedures during each visit.

Medical history

- A complete medical history, including history of diabetes, will be taken at screening. The subject's medical history will be updated at the Baseline visit. This updated medical history will serve as the baseline for clinical assessment.
- Demographic information, including subject self-reported gender, race, age, ethnicity, and child-bearing potential will be recorded.
- Nicotine and alcohol history will be obtained

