Laboratory reference ranges will be obtained prior to the initiation of the study. The Baseline laboratory test results for clinical assessment for a particular test will be defined as the last measurement prior to the initial dose of study drug.

Whether action needs to be taken to address notable laboratory values will be decided by the investigator, taking into account the overall status of the subject.

The following laboratory tests will be performed according to the study procedures schedule listed in Overview of Study Procedures:

- Complete Blood Count (CBC): automated WBC, RBC, hemoglobin, hematocrit, platelet count

and RBC indices

- Complete Metabolic Panel (CMP): Sodium, Potassium, Chloride, Bicarbonate, BUN, Creatinine, Glucose, Alk Phos, ALT, AST, Total Bilirubin, GGT, Albumin, Albumin/Globulin Ratio (calculated), BUN/Creatinine Ratio (calculated), Calcium, Globulin (calculated), Total Protein
- HIV: HIV1&2 Antibody/Antigen Combo Assay
- Hepatitis B: Hep B Core Ab (Hep B Cab), Hep B Surface Antigen (Hep B Sag), and Hep B surface antibody (Hep B Sab)
- Hepatitis C: Hepatitis C antibody
- Tuberculosis: Quantiferon-TB Gold

Subjects who test positive for TB (quantiferon gold), Hepatitis C antibody, or Hepatitis B Sag or Hepatitis B Core antibody will be excluded from the study. Patients with a positive quantiferon gold will be referred to ID. If a patient has an indeterminate quantiferon gold that test will be repeated. If there are two indeterminate quantiferon gold results, then the patient will be referred to ID. If ID thinks the patient (with an indeterminate quant gold) needs to be treated for latent TB, then the patient will be treated for latent TB (see below). If ID does not think the patient (with an indeterminate quant gold) needs treatment for latent TB then the patient will be eligible to enroll in the clinical trial

After one month of treatment for latent TB, a subject would be considered eligible for participation in the trial.

Skin Biopsy

A 4 mm punch biopsy will be obtained from lesional skin at the baseline and week 26 visit. Skin biopsy location will be determined by the investigator and standard procedures for skin biopsy will be employed. Subjects may have lesions closed with suture or gelfoam, depending on nature of lesion and biopsy.

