Skin biopsies will be sent to Dermatopathology lab at BIDMC for further Immunohistochemistry analysis as below. Samples will be preserved in formalin jars and sent to the histology lab to be processed within 48 hours. The paraffin blocks will be sectioned and stained at the histology lab, and then blocks and slides will be returned to the Dermatopathologist and stored securely at BIDMC, Dept of Pathology. Samples are retained for the duration of the project, through publication. If all

members of the study team deem they are no longer needed, they will then be destroyed.

Immunohistochemistry

Each biopsy will be fixed in formalin, bisected vertically, dehydrated by routine histologic methods, and embedded in a paraffin block. 5- μ m-thick surface sections will be cut, mounted on glass slides, and baked for 60 minutes at 60C. The first slide will be stained with Hematoxylin and Eosin. The next slide will be loaded into the Bond III staining platform and antigen retrieved by immersion in Bond Epitope Retrieval 2 for 30 minutes. It will then incubated at room temperature for 30 minutes with Anti-Human IL17A antibody [Abcam 4K5F6] at a concentration of 0.5–10 μ g/ml. After appropriate washes, antibody detection will be performed using Bond Polymer Refine Detection kit. Slides will be developed in DAB, then dehydrated and coverslipped. A biopsy of an active psoriatic skin lesion and a slide of the case with no antibody applied will be run in parallel as positive and negative controls, respectively.

Evaluation of immunohistochemistry

IL-17A expression levels will be scored as follows: A three tier stratification threshold for percentage of positive lymphocytes will be established after review of the pre-treatment biopsies, and classified as absent, low, or high. Cellular staining intensity will be scored as 0 (no staining), 1 (weak staining), 2 (moderate staining), or 3 (strong staining).

Pre- and post-treatment expression levels will be compared using Fisher's exact test. Pre-treatment IL17A expression level will be compared with clinical response parameters and evaluated as a possible predictor of response to therapy.

In case of an adverse event or disease progression, patients are instructed to call and/or visit the clinic trials unit at Beth Israel Deaconess Medical Center. Any visits will be recorded on source documentation as Unscheduled Visits. Any of the procedures may be performed at an unscheduled visit at the discretion of the investigator.

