The clinical efficacy will be measured by physician assessments and standardized scoring tools as noted in Main Study Parameters and Secondary Parameters. Because of the small number of patients in the study, and absence of a control group, primarily descriptive statistics will be used to report data from measured endpoints.

Main Study parameters

Primary Endpoint

- Proportion of patients achieving remission or clinical improvement based on Investigator Global Assessment Score as measured at week 24.

We will assess the proportion of patients achieving remission or clinical improvement based upon the previously published Investigator Global Assessment Score. Remission correlates with a score of 0 or 1 and clinical improvement correlates with at least a -1 change from baseline.

Secondary study parameters

Secondary Endpoints

Because of the small sample size, primarily descriptive statistics will be used.

- Proportion of subjects achieving improvement based upon histological score
- Proportion of subjects achieving improvement based upon patient-reported outcomes (pain score and Dermatology Quality of Life Index Score)

Other study parameter(s)

Patient characteristics and demographic data will be presented using descriptive statistics.

Histological Score

In addition, a histological score will be calculated as a secondary endpoint. The score is calculated by adding sub scores as listed below, which will be evaluated by the dermatopathologist. Average of pre and post scores and overall change in score will be calculated and compared using a paired T-test. See Secondary Study Parameters for details regarding histologic analysis.

Pain Score

A Pain Score will be calculated based upon the Wong-Baker 10-point pain score, which has been widely used to rate pain in both children and adults and has also been used in dermatology clinical trials.[6]

Response based on an improvement from baseline in the Wong-Baker pain score at all scheduled time points will be calculated. We will compare pre and post treatment pain values and categorize patients as

Dermatology Life Quality Index (DLQI)

A Quality of Life Score will be calculated based upon the Dermatology Life Quality Index (DLQI).

C. Subject Selection

Inclusion Criteria

A subject must meet all of the following criteria in order to be eligible to participate in this study:

1. Adults, age 18 and over
2. Previous diagnosis of biopsy-proven NLD
3. Active NLD lesions, defined as

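### IL-17A levels before and after treatment come from the same subjects, but the plan compares them with Fisher's exact test, which is not a paired test

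*Combined protocol and SAP*

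**What the plan says.** The sentence at issue is in B3.A, Evaluation of immunohistochemistry: "Pre- and post-treatment expression levels will be compared using Fisher's exact test". The same section defines two ordered scores for each biopsy. The percentage of positive lymphocytes is "classified as absent, low, or high", and staining intensity is graded 0 to 3. It does not say which score is tested or which table Fisher's test is applied to.

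Other sections settle where the data come from:

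- B3.A, Randomization, blinding and treatment allocation: "All subjects will receive study treatment". There is no control group.
- B3.A, Skin Biopsy: "A 4 mm punch biopsy will be obtained from lesional skin at the baseline and week 26 visit". The schedule of procedures marks the second biopsy at week 24. The two should be reconciled, but pairing is unaffected.
- The same section: "Skin biopsy location will be determined by the investigator". The same lesion need not be sampled twice.

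The only paired method in the plan is in B3.B, Histological Score, where "overall change in score will be calculated and compared using a paired T-test". That score sums four items, of which IL-17 expression (item d, graded 0 to 3) is one. B3.B, Study Parameters, says that "primarily descriptive statistics will be used to report data from measured endpoints".

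**The concern.** Both IL-17A values in a comparison come from one subject, and there is no second group. Fisher's exact test can be set up in two ways, and neither tests within-subject change.

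- **Table A, time point by level** (the more natural reading). This addresses the marginal shift, but it treats 18 pairs as 36 independent biopsies. Its p-value cannot tell a consistent fall from movement in both directions, and it is miscalibrated for paired data.
- **Table B, baseline level by post-treatment level.** This keeps the pairs, but it tests whether the two levels are associated. Subjects who never change produce a very small p-value.

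IL-17 is the rationale for the study, and this is the only planned test that isolates it before and after treatment. The summed histological score cannot take its place, because a change there may come from the other three items. At stake is whether a reported p-value for the effect on the target means what a reader will take it to mean.

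**Working it through.** The plan gives no power, alpha or effect size for this comparison, so there is no stated figure to reproduce. From the documents come the planned 18 subjects (at most 18 pairs) and the single-arm design. Everything else is an illustrative assumption: IL-17A reduced to high or not high, two-sided 0.05, and a within-subject correlation phi that the documents do not give.

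**1. Single tables (no correlation assumed).** Take 18 pairs, 12 high before and 6 high after. Table A is [[12, 6], [6, 12]], and Fisher gives p = 0.094 whatever the pairs did. The exact McNemar p-value is 2 × P(X ≤ smaller count), with X binomial on the changing pairs and probability 1/2:

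| Fall / rise | Calculation | Exact McNemar |
|---|---|---|
| 6 / 0 | 2 × 1/64 | 0.031 |
| 9 / 3 | 2 × 299/4096 | 0.146 |
| 12 / 6 | 2 × 31180/262144 | 0.238 |

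**2. Very few pairs.** If four of four fall, Fisher on Table A gives 2/70 = 0.029, while the exact paired p-value is 2 × (1/2)^4 = 0.125. The smallest attainable paired p-value with 3, 4, 5 or 6 changing pairs is 0.25, 0.125, 0.0625 or 0.031.

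**3. Table B.** With eight subjects high twice, eight not high twice and one moving each way, there is no net change. Fisher gives 0.003 and McNemar 1.0. With nine high twice and nine not high twice, nobody changes, and Fisher gives 0.00004.

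**4. Power, by full enumeration of the paired 2×2 outcomes.** The share high falls from 70% to 30%. The cell for high at both times is 0.7 × 0.3 + phi × 0.21, because sqrt(0.7 × 0.3 × 0.3 × 0.7) = 0.21. That cell cannot exceed 0.30, so phi is at most 0.09/0.21 = 0.43.

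| Pairs | phi 0: Fisher A v McNemar | phi 0.2 | phi 0.4 |
|---|---|---|---|
| 18 | 60.9 v 53.2% | 61.7 v 62.9% | 62.6 v 76.6% |
| 12 | 38.9 v 29.5% | 37.1 v 32.1% | 34.3 v 33.5% |
| 8 | 24.6 v 9.4% | 21.5 v 7.4% | 17.9 v 5.3% |

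At 18 pairs the two tests cross at phi of about 0.18.

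**5. Rejection with no change** (50% high at both times, 18 pairs). Fisher on Table A rejects 2.9, 1.5 and 0.5% at phi 0, 0.2 and 0.4. It exceeds 5% only with negative correlation (5.6% at phi −0.3). Fisher on Table B rejects 2.7, 8.1 and 28.8% at the same phi of 0, 0.2 and 0.4. For the real fall from 70% to 30% it rejects only 2.1, 3.3 and 14.7%.

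**The case against.** The strongest reply is that the mismatch is real but does little harm. Four parts of it deserve an answer.

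- **Error rate.** Fisher on Table A is conservative unless the two biopsies are negatively correlated. With four pairs and 50% high it rejects 0.8% of the time at phi 0, and reaches 12.5% only at phi −1. This stands. The contrast of 0.029 with 0.125 shows what an exact paired analysis can support once all four pairs have changed. It does not show an inflated error rate for uncorrelated or positively correlated biopsies.
- **Power.** The advantage of the paired test at 18 pairs (76.6 v 62.6%) uses phi 0.4, close to the maximum of 0.43 for that scenario. At phi 0 Fisher leads, and at 8 and 12 pairs it leads at every phi shown. This also stands, so the case for change should not rest on power.
- **Role of the analysis.** The comparison is not a listed endpoint and carries no alpha, and the plan is mainly descriptive. B3.A mentions three completers and one early termination, without saying that enrolment has closed. With three pairs Fisher on Table A cannot go below 0.10. This limits the consequence, but the plan still names a test, so a p-value is to be expected.
- **Table B.** Nothing in the text says that this table will be used. That is true. Its figures matter only because the plan leaves the table unspecified.

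None of this makes Fisher's test a test of paired change.

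**Conclusion.** The concern holds. As written, the plan assigns an unpaired test to paired data, and no other section supplies a paired method for IL-17A. This is a wrong method, not merely a missing detail. The finding itself needs no assumption about correlation: for the same margins Fisher on Table A stays at 0.094 while the exact paired p-value runs from 0.031 to 0.238.

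The direction of the error is not fixed. At 18 pairs with phi above about 0.2, Fisher on Table A loses power. With few pairs it rejects more often than the paired test. If Table B is used, the p-value answers a different question. The power and rejection rates rest on the two-level score, the chosen shares and the assumed phi.

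The primary endpoint is untouched, and IL-17 item d could still be described subject by subject. The correction should be made because it is cheap and concerns the one test aimed at the drug's target. It does not threaten the study's main conclusion.

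**What to change.** Replace the sentence in Evaluation of immunohistochemistry with:

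> Within-subject change in IL-17A tier (absent/low/high) will be tested with the two-sided exact sign test, comparing the number of subjects whose tier fell with the number whose tier rose (exact McNemar on a two-level score). The same test on staining intensity (0–3) is supportive, without multiplicity adjustment. The pre-by-post shift table and each subject's change will be reported. With fewer than six changing pairs no two-sided exact paired p-value can reach 0.05, so the result is then descriptive.

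The exact Wilcoxon signed-rank test is an alternative if the investigators accept that a step from absent to low may be ranked equal to a step from low to high. Putting tier ahead of intensity is a choice that the current text leaves open; either order works if it is fixed in advance.

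The cost is four sentences, using only scores already collected. The downside is that the paired test rejects less often than Fisher when pairs are few or the two biopsies are nearly uncorrelated.

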Follow up phone call at Week 36

Study personnel will call subjects to collect information regarding the status of any ongoing AEs/SAEs or the occurrence of any new AEs/SAEs since last study visit.

EARLY TERMINATION VISIT

If a subject is withdrawn from the study for any reason, including withdrawing informed consent, he/she will be asked to return for an early termination visit within 2 weeks of being withdrawn from the study. Procedures performed at Early Termination Visit will be identical to Week 26 visit.

Treatment of Subjects

Investigational Treatment: Secukinumab (Cosentyx)

Secukinumab (Cosentyx) is a human monoclonal antibody that targets IL-17a and is FDA-approved for the treatment of psoriasis, psoriatic arthritis, and ankylosing spondylitis. Recent literature expanding on the previously poorly understood pathogenesis of NLD has suggested a potential role for IL-17 in the development of this condition. Thus blockade of IL-17 may be a potential therapeutic strategy in patients with NLD

Dosage

Dosage of Secukinumab will be given according to the standard therapy regimen for psoriasis and administered for 24 weeks. Each subject will receive 300mg of Secukinumab by using 2 syringes of 150mg each as a subcutaneous injection at weeks 0,1,2,3,4 then every 4 weeks for a total of 9 doses over 24 weeks. Medication will be administered during scheduled study visits by study personnel.

Use of Co-intervention

Co-medication

A full list of current medication, including over-the counter medicines, will be noted for each subject at time of screening visit and will updated at each visit in their medical chart/report form.

Analgesic Therapy

If a subject develops more than transient pain or the subject's pain increases after starting treatment, they are allowed to start analgesic therapy. In case of NLD-related pain, the subject will be asked to report this at the next visit.

Exacerbation/Intervention

In case exacerbations of NLD lesions occur in the treatment areas and an intervention is required, the investigator may decide to treat with standard therapies not anticipated to decrease size of active areas such as antibiotics. Use of any of the prohibited treatments listed below could that could

confound the efficacy assessment are NOT allowed during the study. If the subject requires treatment with any of the prohibited treatments listed below, the subject should be discontinued from the study treatment will proceed to an early termination visit.

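### The pain endpoint ignores analgesics that may be started on study, so a score lowered by an analgesic can count as pain improvement

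*Combined protocol and SAP*

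**What the plan says.** **Analgesics.** Under Use of Co-intervention in section B3.A, an analgesic may be started in two situations: pain that is new and not merely passing, or pain that rises on treatment ("pain increases after starting treatment, they are allowed to start analgesic therapy"). The next sentence adds "In case of NLD-related pain, the subject will be asked to report this at the next visit", and attaches no consequence for scoring.

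**Treatments that disturb efficacy.** The same section deals with these only through the prohibited list: "If the subject requires treatment with any of the prohibited treatments listed below, the subject should be discontinued from the study treatment". That list covers investigational agents, systemic immunosuppressants and surgery on the treated areas. Analgesics are not on it, so a subject who starts one stays on study and continues to be scored.

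**Pain endpoint.** Improvement in pain is part of a secondary endpoint. Section B3.B, Pain Score, states "A Pain Score will be calculated based upon the Wong-Baker 10-point pain score", then "Response based on an improvement from baseline in the Wong-Baker pain score at all scheduled time points will be calculated", then "We will compare pre and post treatment pain values and categorize patients as". That last sentence breaks off in the text available. The four categories stand under Patient-Reported Outcomes in section B3.A, without numeric cut-offs.

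**Data collected.** Under Co-medication, "A full list of current medication, including over-the counter medicines, will be noted for each subject at time of screening visit", with updates at each visit. The Overview of Study Procedures schedules both the pain score and concomitant therapy at baseline and at every visit through Week 24.

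**The concern.** An analgesic lowers the variable that the pain endpoint measures, and one reason for allowing it is an unfavourable value of that same variable. If the later score enters the analysis unmarked, the endpoint credits secukinumab with relief that may have come from the analgesic. In a randomised trial, a comparison of arms would at least show whether analgesic use differed between them. Here every subject receives secukinumab, and the reported proportion is itself the result.

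The protocol already accepts the principle for lesions. Under Exacerbation/Intervention it limits treatment to measures not expected to shrink active areas, and it bars listed treatments because they could confound efficacy. The pain endpoint has no matching protection in the analysis.

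**Working it through.** The plan gives no pain response rate, power or interval to reproduce, and it states that no sample size calculation applies. The check therefore follows the rules and then sizes one reclassified subject.

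**Step 1: what the rule returns.** These scores are invented for illustration; the categories are read in their ordinary sense.

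| Baseline | Week 8 | Analgesic started after Week 8 | Week 24 | Pre/post category |
|---|---|---|---|---|
| 4 | 8 | yes | 2 | Improved |
| 4 | 8 | yes | 0 | Resolved |
| 4 | 8 | yes | 4 | Stable |
| 4 | 8 | no | 8 | Worsened |

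The first two rows add a responder. The third does not, but it hides a worsening. The by-visit scores would show the rise at Week 8. They would not show that the later fall followed an analgesic.

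**Step 2: size of one subject.** Planned enrolment is 18 (section B3.A): 1/18 = 5.6 points. The follow-up call paragraph mentions 3 completers and 1 early termination, so 3 + 1 = 4, and 1/4 = 25 points if only these are analysed.

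**Step 3: an assumed count.** Suppose 9 of 18 are classed as improved, and k of those 9 were using an analgesic started on study. With exact (Clopper-Pearson) 95% intervals:

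| k | Proportion after reclassification | 95% interval |
|---|---|---|
| 0 | 9/18 = 50.0% | 26.0 to 74.0% |
| 1 | 8/18 = 44.4% | 21.5 to 69.2% |
| 2 | 7/18 = 38.9% | 17.3 to 64.3% |
| 4 | 5/18 = 27.8% | 9.7 to 53.5% |

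**Step 4: an assumed range for the total.** Let p be the true improvement rate, r the share of non-improvers who start an analgesic, and m the share of those who then score below baseline. The inflation is (1 − p) × r × m.

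- Low end (p = 0.5, r = 0.1, m = 0.25): 0.5 × 0.1 × 0.25 = 0.0125, or 1.25 points.
- High end (p = 0.3, r = 0.3, m = 1): 0.7 × 0.3 × 1 = 0.21, or 21 points.

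None of p, r and m is in the protocol. The formula also leaves out any error in the other direction, such as a baseline analgesic that is stopped.

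**The case against.** **Scoring pain regardless of analgesics is a legitimate choice.** It is, if the plan says so and the reader can see who used them. This plan does neither. Reporting the as-observed result beside the stricter one keeps that choice available.

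**Pain is scored at every visit, so a rise would be seen.** This partly stands: by-visit response would record non-response at the visit with the higher score. If the response sentence were read as requiring improvement at every visit, such a subject would not be a responder on that measure at all. The pre/post category is unaffected on either reading.

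**The bias may not run one way.** This stands. A reader might infer that every error favours secukinumab. The plan neither bars analgesics at baseline nor requires a stable dose. A subject who stops one because the lesion has improved may score Stable, which counts against the drug. A fall after an analgesic is also not proof that the analgesic caused it, since secukinumab continues through Week 20.

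**The trigger is not limited to worsening NLD pain.** This stands too. New pain qualifies, and the permission does not restrict the cause, so biopsy or injection pain could be included. It would be wrong to read the permission as applying only to subjects whose disease pain rose on the drug.

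**The consequence is small.** Pain is one component of a secondary endpoint in an uncontrolled, mainly descriptive pilot. The primary endpoint is a global assessment not defined by pain. One subject's shift is also small beside the intervals in the working. That limits the weight of the point. It does not remove it, because the shift is a classification error that the collected data could prevent.

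**Conclusion.** The point holds in a limited form. As written, the pain classification takes no account of analgesics that the protocol allows to be started, so the proportion with improved pain can be inflated. That the score under analgesic is the one used is an inference: the plan compares scores before and after treatment and sets no condition on analgesic use. A subject becomes a false responder only if the score falls below baseline.

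The supported size is 5.6 points per such subject at 18, or 25 points at 4. A reader might take the background statement that about 25% of patients have very painful lesions and expect 4 to 5 of 18 to be affected (18 × 0.25 = 4.5). The protocol does not support that step. The figure describes NLD patients in general, not analgesic starts on study, and enrolment requires active lesions. The range of 1.25 to 21 points rests wholly on assumed inputs.

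The DLQI covers symptoms and could be affected in the same way, but nothing in the protocol shows by how much. The point is worth correcting before the pain results are reported and does not touch the primary endpoint.

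**What to change.** Add to the Pain Score paragraph of section B3.B:

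- A subject who has started or increased an analgesic for NLD pain after baseline, and is still using it at a visit, is not counted as Resolved or Improved at that visit.
- The as-observed classification is reported beside this one.
- Analgesic use is listed by subject and visit from the concomitant medication record, including use at baseline and any reduction or stopping, so that errors in either direction can be seen.
- The same subjects are flagged in the DLQI table.
- The rule is labelled as added after the first subjects had completed, since the protocol already mentions three completers and one early termination.

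Because the rule works visit by visit, it applies whichever visit is taken as post-treatment.

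**Cost.** The text is short and needs no new visits or assessments. The work lies in reading indication, timing and dose increases from the medication record. The protocol promises a medication list but does not mention as-needed use, so some entries may need a query. A subject who truly improved while still using an analgesic is counted conservatively, which is why both classifications are shown. The permission to use analgesics is unchanged.
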